6.4 Dose Delay/Modifications Guidelines for Pralatrexate-Associated Adverse Events

Pralatrexate dose modifications will be allowed according to the criteria outlined in Table 6.4.1, Table 6.4.2, and Table 6.4.3.

Exceptions:

- For patients who develop severe renal impairment (eGFR or CrCl 15 to < 30 mL/min/1.73m²) while on treatment with pralatrexate at the 30 mg/m² dose level, the dose of pralatrexate upon recovery will be reduced to 15 mg/m².
- For patients who develop severe renal impairment (eGFR or CrCl 15 to < 30 mL/min/1.73m²) while on treatment with pralatrexate at the 20 mg/m² dose level or lower, pralatrexate will be permanently discontinued.

Treatment may be delayed to allow sufficient time for recovery. Patients whose treatment is delayed because of pralatrexate-related toxicity should be evaluated at weekly intervals (or less) until adequate recovery has occurred. A patient who has not received pralatrexate for more than 28 days since last study drug administration should be discontinued from further pralatrexate treatment. Any patient who requires a pralatrexate dose modification due to toxicity should continue to receive the modified regimen for the remainder of the study unless agreed otherwise with the overall study PI or their designee. For patients who require a pralatrexate dose reduction, for any reason, leucovorin should continue to be administered at the specified dose and schedule. For patients who require doses of pralatrexate to be omitted due to mucositis (Table 6.4.1), leucovorin dosing should continue per protocol. For patients who require doses of pralatrexate be omitted for an adverse event other than mucositis or stomatitis (Table 6.4.2 and Table 6.4.3), leucovorin treatment should be stopped until the patient resumes pralatrexate treatment. Safety assessment and routine clinical care should be followed at all times.

Table 6.4.1 Dose Modifications for Mucositis, based on NCI CTCAE Version 5.0

Mucositis Grade on Day of Treatment	Action	Dose Upon Recovery to ≤Grade 1
Grade 2	Omit pralatrexate dose	Continue prior pralatrexate dose
Grade 2 recurrence	Omit pralatrexate dose	Reduce pralatrexate by one dose level (e.g. should be lowered to 20 mg/m ² if receiving 30 mg/m ² , 15 mg/m ² if receiving 20 mg/m ²)
Grade 3	Omit pralatrexate dose Hold pembrolizumab	Reduce pralatrexate by one dose level Resume pembrolizumab
Grade 4	Permanently discontinue pralatrexate Hold pembrolizumab	If not probably or definitely related to pembrolizumab, pembrolizumab resumption can be considered in discussion with Study PI

Table 6.4.2 Dose Modifications for Hematologic Toxicities

Blood Count on Day of Treatment	Duration of Toxicity	Action	Dose Upon Restart
Platelet ≤25,000/µL	1 week	Omit pralatrexate dose Hold pembrolizumab	Continue prior pralatrexate dose Resume pembrolizumab
	2 weeks	Omit pralatrexate dose Hold pembrolizumab	reduce pralatrexate by one dose level Resume pembrolizumab
	3 weeks	Permanently stop pralatrexate Hold pembrolizumab	Pembrolizumab resumption can be considered in discussion with Study PI
ANC 500-1,000/µL with fever OR ANC <500/µL	1 week	Omit pralatrexate dose, give GCSF support Hold pembrolizumab	Continue prior pralatrexate dose with GCSF support Resume pembrolizumab
	2 weeks or recurrence	Omit pralatrexate dose, give GCSF support Hold pembrolizumab	reduce pralatrexate by one dose level with GCSF support Resume pembrolizumab
	3 weeks or 2 nd recurrence	Permanently stop pralatrexate Hold pembrolizumab	Pembrolizumab resumption can be considered in discussion with Study PI

ANC= absolute neutrophil count, GCSF=granulocyte colony stimulating factor, GMCSF= granulocyte macrophage colony stimulating factor.

Table 6.4.3 Dose Modifications for all Other Pralatrexate-Related Toxicities

Toxicity Grade On Day of Treatment	Action	Dose Upon Recovery to ≤Grade 1
Grade 3	Omit pralatrexate dose	reduce pralatrexate by one dose level
Grade 4	Permanently stop pralatrexate therapy	---

7.0 REPORTING OF ADVERSE EVENTS, UNANTICIPATED PROBLEMS & OTHER EVENTS OF INTEREST

The research team is responsible for classifying adverse events (AEs) and unanticipated problems (UPs) as defined in the relevant regulations and reporting to all applicable parties, including but not limited to the COH IRB, DSMC, Food and Drug Administration (FDA), National Institutes of Health (NIH) and other collaborators, e.g., pharmaceutical companies. The research team is responsible for the continued monitoring and tracking of all AEs in order to ensure non-reportable events are reviewed and monitored and do not rise to a reporting level.

7.1 Assessment of Adverse Events

The site Investigator will be responsible for determining the event name, and assessing the severity (i.e., grade), expectedness, and attribution of all adverse events as applicable per the [City of Hope Clinical Research Adverse Event and Unanticipated Problem policy](#) (available from the DCC). Adverse events will be characterized using the descriptions and grading scales found in NCI CTCAE v5.0. A copy of the scale can be found at:

https://ctep.cancer.gov/protocoldevelopment/electronic_applications/ctc.htm.

The following definitions will be used to determine the causality (attribution) of the event to the study agent or study procedure.

- **Unrelated** – The event is clearly NOT related to study treatment, and is clearly related to other factors such as the participant's clinical state, other therapeutic interventions, or concomitant medications administered to the participant.
- **Unlikely** – The event is unlikely related to the study treatment, and is most likely related to other factors such as the participant's clinical state, other therapeutic interventions, or concomitant drugs.
- **Possible** – The event may be related to study treatment, as it follows a reasonable temporal sequence from the time of drug administration, but could have been produced by other factors such as the participant's clinical state, other therapeutic interventions, or concomitant drugs.
- **Probable** – The event is most likely related to the study treatment, as it follows a reasonable temporal sequence from the time of drug administration and a known response pattern to the study drug, and is unlikely related to the participant's clinical state, other therapeutic interventions, or concomitant drugs.

Definite – The event is clearly related to the study treatment, as it follows a reasonable temporal sequence from the time of drug administration and a known response pattern to the study drug, and is not reasonably explained by other factors such as the participant's condition, therapeutic interventions, or concomitant drugs.

7.2 Secondary Malignancy

A secondary malignancy is a cancer caused by treatment for a previous malignancy (e.g., treatment with investigational agent/intervention, radiation or chemotherapy). A secondary malignancy is not considered a metastasis of the initial neoplasm.

The investigator must immediately notify the Study PI/ DCC via an expedited report.

7.3 Adverse Events of Special Interest (AESI) Requiring Expedited Reporting

7.3.1 Immune-related AEs

An immune-related adverse event (irAE) is defined as an adverse event that is associated with drug exposure and is consistent with an immune-mediated mechanism of action and where there is no clear alternate etiology. Serologic, immunologic, and histologic (biopsy) data, as appropriate, should be used to support an irAE diagnosis. Appropriate efforts should be made to rule out neoplastic, infectious, metabolic, toxin, or other etiologic causes of the irAE.

7.3.2 Overdose

For purposes of this trial, an overdose of pembrolizumab will be defined as any dose of 1,000 mg or greater (≥ 5 times the indicated dose). No specific information is available on the treatment of overdose of pembrolizumab. Appropriate supportive treatment should be provided if clinically indicated. In the event of overdose, the subject should be observed closely for signs of toxicity. Appropriate supportive treatment should be provided if clinically indicated.

No specific information is available on the treatment of pralatrexate overdosage. If an overdose occurs, general supportive measures should be instituted as deemed necessary by the treating physician. Although there has been no formal or definitive evaluation of the effect of leucovorin following an overdose of pralatrexate, it has been established in clinical studies that leucovorin reduces pralatrexate toxicity, and based on the mechanism of action of pralatrexate, the prompt administration of leucovorin should be considered.

7.3.3 Abnormal Liver Function Tests

An elevated AST or ALT lab value that is greater than or equal to 3X the upper limit of normal and an elevated total bilirubin lab value that is greater than or equal to 2X the upper limit of normal and, at the same time, an alkaline phosphatase lab value that is less than 2X the upper limit of normal, as determined by way of protocol-specified laboratory testing or unscheduled laboratory testing.

These criteria are based upon available regulatory guidance documents. The purpose of the criteria is to specify a threshold of abnormal hepatic tests that may require an additional evaluation for an underlying etiology.

7.4 Pregnancies

Although pregnancy and lactation are not considered adverse events, it is the responsibility of investigators or their designees to report any pregnancy or lactation in a subject (spontaneously reported to them) that occurs during the trial.

Efforts must be made by the investigator to follow the outcome of pregnancy outcome per institutional policies.

Pregnancy outcomes of spontaneous abortion, missed abortion, benign hydatidiform mole, blighted ovum, fetal death, intrauterine death, miscarriage and stillbirth must be reported as serious events (Important Medical Events). If the pregnancy continues to term, the outcome (health of infant) must also be reported. If the newborn is healthy additional follow-up is not necessary.

Any pregnancy related event described above must be reported to the Study PI/ DCC immediately within 24 hours of awareness. Protocol therapy is to be discontinued immediately.

7.5 Adverse Event (AE) collection guidelines

- During Cycles 1 & 2, all grade toxicities with start and stop dates will be reported in the eCRFs.
- After Cycle 2 until the end of the safety follow-up period (30-days post-last dose for AE or 90 days post-last dose for SAE), the highest grade AND all Grade 3+ toxicities (regardless of whether highest grade or not) per cycle and all SAEs with start/stop dates will be reported in the eCRFs.

7.6 Routine AE Collection and Reporting Guidelines

AEs will be collected from the signing of informed consent until ending study participation. Routine AE reporting will occur via data entry into the study eCRF. AEs will be monitored by the Protocol Management Team (PMT). AEs reported through expedited processes (e.g., reported to the IRB, FDA, etc.) must also be reported in routine study data submissions.

AEs recorded in the CRF include:

- All events considered unrelated, unlikely, possibly, probably or definitely related to protocol therapy.
- Any Grade 1-5 during the DLT period (cycles 1 and 2), the highest grade AND all Grade 3+ toxicities (regardless of whether the highest grade or not) after cycle 2 during each cycle and during the safety follow-up period.
- All SAEs.

7.7 Expedited Reporting

Table 7.7 indicates what events must be reported expeditiously.

Table 7.7 Criteria for Expedited Reporting

Time point	What to report expeditiously
From the signing of the consent to study completion	All unanticipated problems
From Screening until Day 1 of protocol therapy	
 • All SAEs related to protocol procedures • Pregnancy and lactation • Any reason for not starting Day 1 of protocol therapy
For the time period beginning at treatment through 90 days following cessation of treatment, or 30 days following cessation of treatment if the subject initiates new anticancer therapy, whichever is earlier	
 • All SAEs regardless of relationship to protocol therapy, study procedure, underlying disease or concomitant treatment. • Death due to any cause other than progression of the cancer under study. • All AEs that meet the definition of an unanticipated problem. • Overdose of either agent. • Pregnancies and lactation. • Abnormal liver function tests • Discontinuation of protocol therapy due to unusual or unusually severe AE considered related to protocol therapy
For participants yet to initiate anti-cancer therapy: From Day 1 of therapy up to 120 days post-last pembrolizumab dose	
 • Pregnancies and lactation.
Post Safety follow-up to removal from study	
 • All SAEs that are considered possibly, probably, or definitely related to pembrolizumab

NOTE: All events reported expeditiously require follow-up reporting until the event is resolved, stabilized, or

determined to be irreversible by the investigator.

The DCC should be consulted prior to ending the follow-up of events that have stabilized.

7.7.1 Expedited reporting guidelines (COH only)

7.7.1.1 To the COH DSMC/IRB

Serious Adverse Events that require expedited reporting and unanticipated problems will be reported according to the approved [City of Hope Clinical Research Adverse Event and Unanticipated Problem policy](#). This includes all SAEs and UPs that meet COH DSMC/IRB expedited reporting criteria that occurred at COH and non-COH sites. For non-COH sites, the DCC will be responsible for reporting (see section 7.7.2)

7.7.1.2 To Participating Investigators

- Report all expedited reportable AEs to participating investigators as an IND Safety Report occurring within 30 calendar days of receipt of sponsor (lead site) notification, and indicate whether or not a protocol and/or consent form change is required. A cover letter will indicate the protocol title, the IND#, whether the FDA was informed (if applicable), and, for non-COH sites, a statement that the report should be submitted to their local IRB for review if applicable per local IRB policy.
- Forward to participating sites all IND safety reports received from Merck and Acrotech Biopharma, LLC, indicating whether a consent form or protocol change is required within 30 days of notification to Study PI.

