7.7.2 Expedited reporting guidelines (non-COH sites only)

7.7.2.1 To the DCC/Study PI

All events that meet the criteria specified in Table 7.7 will be reported to the DCC and Study PI within 24 hours of notification that the event met the expedited reporting criteria.

1. Sites are to report to their local IRB per their site's specific institutional and IRB guidelines. As soon as possible, non-COH sites will provide to the COH DCC copies of the IRB submission and corresponding IRB response.
2. Document/describe the AE/UP on each of the following:
 - a. MedWatch 3500A or local IRB submission document*
MedWatch 3500A is downloadable form at <http://www.fda.gov/medwatch/getforms.htm>
*The local IRB submission document may be used if the document template is approved by the DCC
 - b. Expedited Reporting Coversheet. A modifiable Microsoft Word document is available from the DCC. An electronic signature on the document will be accepted.
3. Scan and email above documents to the Study PI ([contact]) and [contact] with the subject title as "[name] Pembro-PDX SAE COH IRB #17501".
 - a. If available, sites may include the local IRB submission for this event in the submission.
4. If an email receipt from DCC personnel is not received within one working day, please email [contact].

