7.8 Reporting to the FDA

The PI or designee will be responsible for contacting the Office of IND Development and Regulatory Affairs (OIDRA) at COH to ensure prompt reporting of safety reports to the FDA. OIDRA will assist the PI with the preparation of the report and submit the report to the FDA in accordance with the approved [City of Hope Clinical Research Adverse Event and Unanticipated Problem policy](#).

Serious Adverse Events meeting the requirements for expedited reporting to the Food and Drug Administration (FDA), as defined in [21 CFR 312.32](#), regardless of the site of occurrence, will be reported as an IND safety report using the [MedWatch Form FDA 3500A for Mandatory Reporting](#).

The criteria that require reporting using the MedWatch 3500A are:

- Any unexpected fatal or life threatening adverse experience associated with use of the drug must be reported to the FDA no later than 7 calendar days after initial receipt of the information [[21 CFR 312.32\(c\)\(2\)](#)]
- Any adverse experience associated with use of the drug that is both serious and unexpected must be submitted no later than 15 calendar days after initial receipt of the information [[21 CFR 312.32\(c\)\(1\)](#)]
- Any follow-up information to a study report shall be reported as soon as the relevant information becomes available. [[21 CFR 312.32\(d\)\(3\)](#)]

The final IND report will be distributed to the Study PI and DCC. If it is determined that the IND safety report requires a change to the protocol or the consent form, the DCC will include instructions to participating sites for local IRB reporting.

In addition, on behalf of the study PI, OIDRA will submit annually within 60 days of the anniversary date of when the IND went into effect, an annual report to the FDA which is to include a narrative summary and analysis of the information of all FDA reports within the reporting interval, a summary report of adverse drug experiences, and history of actions taken since the last report because of adverse drug experiences.

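### Section 7.7.1.2 allows 30 days to tell participating investigators of events that Section 7.8 sends to the FDA in 7 or 15 days, and nothing else guarantees them earlier notice

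*Combined protocol and SAP*

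**What the plan says.** Section 7.7.1.2 gives the lead site this duty toward the other sites: "Report all expedited reportable AEs to participating investigators as an IND Safety Report occurring within 30 calendar days", counted from the lead site's own notification. The report must say whether the protocol or consent form has to change, and its cover letter must state, where relevant, if the FDA has been told. Safety reports received from the two companies are to be forwarded on a similar limit, "indicating whether a consent form or protocol change is required within 30 days of notification to Study PI".

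Section 7.8 sets shorter limits for the FDA, wherever the event occurred. An unexpected fatal or life-threatening event associated with the drug "must be reported to the FDA no later than 7 calendar days after initial receipt of the information". An associated event that is "both serious and unexpected must be submitted no later than 15 calendar days after initial receipt of the information" falls under the second limit. On internal circulation the section says: "The final IND report will be distributed to the Study PI and DCC". Participating sites receive instructions from the data coordinating center (DCC) only if the report requires a protocol or consent change, and no time limit is given.

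Traffic in the other direction is fast. Under Section 7.7.2.1, events at non-COH sites "will be reported to the DCC and Study PI within 24 hours of notification that the event met the expedited reporting criteria". Section 7.9 gives one company 2 working days and the other 24 hours.

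**The concern.** Both sections use the term IND safety report, but the FDA limits are 7 or 15 days and the limit for treating investigators is 30. For an event that meets the Section 7.8 criteria, the protocol therefore permits a completed FDA report to exist while the other centers' investigators have not been told.

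The protocol describes the regimen as a new combination and runs it at three centers. An unexpected, serious, drug-associated event at one center is information that an investigator elsewhere could use in deciding what to look for before a patient's next administration. Central registration lets the lead site stop new entries, but it does not inform those already treating patients.

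**Working it through.** **Does the 30-day limit cover the FDA-reportable events?** Table 7.7 defines expedited events broadly and includes all serious adverse events on treatment regardless of relationship. The Section 7.8 events are a subset. The cover-letter item on FDA notification confirms that Section 7.7.1.2 contemplates them.

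**Is there a faster guaranteed route to sites?**
- Section 7.8: the final report goes to the Study PI and the DCC; sites hear only if a document must change, with no deadline.
- Section 15.3: site investigators belong to the Protocol Management Team, but its meetings are only recommended and no frequency is set.
- Section 12.3.4: a second possibly related death halts accrual and triggers DSMC review. A first death does not trigger this rule, and it sets no deadline for telling investigators.
- Table 12.1.1, footnote: two DLTs lead to treatment changes for patients on a higher dose. This is confined to DLTs and carries no notification deadline.

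None sets a limit shorter than 30 days.

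**Gap after the FDA deadline**, taking both clocks to start on the same day and each limit to be fully used:
- Unexpected fatal or life-threatening: 30 − 7 = 23 days.
- Other serious and unexpected: 30 − 15 = 15 days.

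**Administrations in the waiting time.** Inputs: pembrolizumab on Day 1 (Section 5.8.1), pralatrexate on Days 1 and 8 (Section 5.8.2), cycles of 21 ± 3 days (Section 5.2). Number days from 0, so that Day 1 is 0 and Day 8 is 7. For cycle length L, notification on day t and waiting time W, count the days d with t < d ≤ t + W. Pembrolizumab is given when d mod L = 0, and pralatrexate when d mod L is 0 or 7. The smallest and largest counts over all possible t are:

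| W (days) | L (days) | Pembrolizumab | Pralatrexate |
|---|---|---|---|
| 30 | 18 | 1–2 | 3–4 |
| 30 | 21 | 1–2 | 2–4 |
| 30 | 24 | 1–2 | 2–3 |
| 15 | 21 | 0–1 | 1–2 |
| 15 | 24 | 0–1 | 0–2 |

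So the full 30-day wait holds at least one pembrolizumab and two pralatrexate administrations at each of these cycle lengths.

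For the 23-day gap with 21-day cycles, 23 ≥ 21, so the window spans a whole period and holds at least one pembrolizumab and two pralatrexate administrations. With 24-day cycles it need not. If the gap covers Days 2 to 24 (24 − 2 + 1 = 23 days), it holds no pembrolizumab and one pralatrexate administration (Day 8).

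**Does a complete new cycle fit into 30 days?** It does for 10 of 21 possible notification days with 21-day cycles, and for 7 of 24 with 24-day cycles. Beyond the 15-day FDA limit only 15 days remain, which is less than one cycle.

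**The case against.** The strongest reply is that the two limits do not contradict each other. Section 7.7.1.2 serves a different recipient, covers far more events, and asks for a judgment on protocol and consent changes. A longer outer limit for that package is understandable. Nothing forbids earlier notice, and the 23 and 15 days arise only if the limits are used to the last day. The management team and the stopping rules also give informal or partial routes. Finally, Sections 7.7.1.1 and 7.8 refer to an institutional adverse-event policy that is not part of the document, and it may set faster practice.

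Most of this stands as a limit on size. It does not supply a guarantee: for the FDA-reported subset, the only stated deadline for notifying all participating investigators is 30 days.

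A reader might infer more than the text supports:
- *That every patient elsewhere receives a full further cycle first.* A complete cycle fits the 30 days only for some notification days, and it cannot fit the 15-day gap. Held doses or single-agent continuation (Sections 5.10 and 6.2) lower the counts further.
- *That the delay covers the immune-related events that the protocol anticipates.* The 7- and 15-day limits apply only to unexpected events. Section 6.1.1 lists many immune-related toxicities as expected, and where they count as such they stay on the 30-day limit even after the change proposed here.
- *That one office holds a finished report back.* Section 7.8 has COH's regulatory office (OIDRA) submit to the FDA; Section 7.7.1.2 names no office.
- *That an outside regulation is breached.* That cannot be judged from the document and is not claimed.

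**Conclusion.** The gap is real but narrow. For unexpected, drug-associated serious events, the protocol permits notice to participating investigators up to 23 days (fatal or life-threatening) or 15 days (other) after the FDA deadline, and no other section guarantees anything sooner. These are maxima, assuming a common start for the two clocks and full use of each limit.

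Measured from lead-site notification, the 30-day wait contains at least one pembrolizumab and two pralatrexate administrations for a patient on both drugs without interruption, with cycles of 18, 21 or 24 days and Day 8 given seven days after Day 1. No minimum of that kind holds for every patient over the 15- or 23-day gap. The point concerns the safety of patients under treatment; it does not affect the endpoints or the sample size.

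**What to change.** Reconcile Section 7.7.1.2 with Section 7.8. Add to Section 7.7.1.2 that any event reported to the FDA under Section 7.8 is sent to all participating investigators no later than its FDA submission. If the need for a protocol or consent change is not yet decided, let that statement follow within the existing 30 days. Keep 30 days for the remaining expedited events.

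The FDA report exists by then, so the cost is earlier distribution and sometimes a second communication. No dose, endpoint, sample size or stopping rule changes. The separate 30-day limit for forwarding the companies' reports is not altered by this change.
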